4.2.3.3 Subgroup analyses of the exploratory endpoints

Subgroup analyses may be repeated as described in Section 4.2.1.8.

4.3 Pharmacodynamic Endpoint(s)

Not applicable.

4.4 Pharmacokinetics

Not applicable.

4.5 Other Exploratory Immunogenicity Endpoints

The following objectives of cellular-mediated and additional immune responses are exploratory and outside the scope of the CSR. Therefore, analyses of these data will not be described in this SAP.

4.5.1 Cellular Mediated Immune Responses

Participants are scheduled to have additional blood samples drawn on Days 1, 8, 29, and 181. The resulting data may be used to evaluate cell-mediated immunity and immune responses using functional/and or phenotypic profiling methods.

4.5.2 Additional Immune Responses

The immunogenicity serum samples taken on Days 1, 29, and 181 may be utilized in other exploratory assays to investigate additional humoral or cellular immune responses based upon emerging safety, efficacy, immunobridging, and immunogenicity data.

4.6 Safety Analyses

The domain safety covers exposure and adverse events.

Unless otherwise stated, the Safety analysis set will be used for this domain.

4.6.1 Exposure

This is a single dose vaccination study with dose administration performed by study site staff. Exposure summaries are not planned, however the number and percentage of participants who receive vaccination is included in the disposition summary described in Section 4.1.1. A listing of exposure details will be provided.

4.6.2 Adverse Events

4.6.2.1 Definitions and Derivations

Adverse events experienced by participants will be collected throughout the study as listed below:

- Immediate unsolicited AEs within 30 minutes of dosing
- Solicited injection site and systemic ARs for 7 days post-vaccination (Day 1 to Day 8)
- Unsolicited AEs for 28 days post-vaccination (Day 1 to Day 29)
- SAEs from date of ICF through 6 months post-vaccination (Day 1 to Day 181)
- MAAEs, AESIs, and deaths over the entire study period (Day 1 to Day 181)

Serious adverse events collected prior to vaccination from ICF will be included in the listings only.

Intensity of AEs is determined by the investigator as mild, moderate, or severe. If there are AEs with missing intensity, the category “Missing” will be summarized separately from the non-missing categories. The relationship of AE to study vaccination will be assessed by the investigator and recorded in the AE eCRF as “Yes” or “No” to the question “Is this event related to study medication?” If there are AEs with missing relationship, the category “Missing” will be summarized separately from the non-missing categories. Partial or missing dates for AEs, SAEs, AESIs, and MAAEs will be imputed as described in Appendix B. Duration of AEs will not be calculated using imputed dates and will instead be set to missing in the listings.

Solicited ARs that are present on the last eDiary completion date (Day 8) may not have resolved on Day 8. The solicited ARs which have not resolved at Day 8 will be marked as a continuing event and documented as an unsolicited AE in the AE eCRF in order to collect the stop date of the adverse reaction. However, the continuing event will not be summarized as an unsolicited AE to avoid duplication. The start date for the continuing event will be the first day the solicited AR was first recorded in the eDiary; the stop date will be recorded in the AE eCRF. The duration of solicited ARs will be calculated as the last day of the adverse reaction – the first day of the adverse reaction + 1. Participants with a missing stop date for a solicited AR will not be included in the calculation of duration and will instead be summarized as missing.

The severity of solicited ARs is collected directly in the eDiary except for fever, erythema/redness, and induration/swelling where the severity will be categorized programmatically as, mild (Grade 1), moderate (Grade 2), or severe (Grade 3) based on comparison of the temperature and diameter measurements recorded in the eDiary against the grade ranges provided in the appendix of the CSP. Measurements below the lower limit of the mild category will be categorized as “none” and will be excluded from duration summaries. A severity of potentially life-threatening is not collected in the eDiary and would instead be recorded as an SAE based on investigator assessment. For solicited ARs that are ongoing after Day 8, the maximum severity will be summarized over the entire duration of the event.

Adverse events of special interest are defined in the CSP and the data will be taken directly from the AE eCRF.

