1.3 Schedule of Activities

Table 1 Schedule of Activities

Procedure	Vaccination and Follow-up Period				Details in Protocol Section or Appendix
Visit number	1	2	3	4	
Visit Day (window) days	1 (N/A)	8 (+2)	29 (+3)	181 (± 14)	
Visit type	Clinic	Clinic	Clinic	Clinic	
Informed consent ^a	X (pre-dose)				Section 5.1
Demography and Medical history	X (pre-dose)				Sections 5.1 and 5.2
Targeted physical examination based on medical history	X (pre-dose)				Section 8.3.1
Height, Weight	X (pre-dose)				Section 8.3.2
Body temperature, Blood pressure	X (pre-dose)				Section 8.3.2
Verify eligibility criteria	X (pre-dose)				Sections 5.1 and 5.2
Randomization	X (pre-dose)				Section 6.3
Immunogenicity serum sample	X (pre-dose)		X	X	Section 8.9.1
Blood sample for cell-mediated immune responses	X (pre-dose)	X	X	X	Section 8.9.2
Vaccine administration	X				Sections 6.1 and 6.2
Immediate post-vaccination assessment ^b	X				Section 8.3.5.1
eDiary distribution and training for solicited ARs	X				Section 8.4.6
Solicited ARs ^c	X (ongoing through Day 8)				Section 8.4.6
eDiary collection		X			Section 8.4.6
Unsolicited AEs	X				Section 8.4.1 and 8.4.2
SAEs/AESIs/MAAEs	X				Section 8.4.1, 8.4.2, 8.4.7, 8.4.8, and 8.4.10
Concomitant medications ^d	X				Section 6.9

^a Confirm consent form signed prior to any procedures.

^b Immediate unsolicited AEs to be collected during the 30-minute observation period following vaccination.

^c Predefined solicited ARs recorded by participant in eDiary to assess reactogenicity. Investigators are to follow-up on any solicited ARs that are ongoing at Day 8 through to their resolution (see [Sections 8.4.6 and 9.4.3](#)).

^d All concomitant medications will be recorded in the source documents. Prohibited medications and any medications used to treat SAEs or AESIs will also be recorded in the eCRF.

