8.4.6 Solicited Adverse Reactions (Reactogenicity)

Solicited injection site and systemic predefined ARs will be collected in a solicited AR reactogenicity eDiary for all participants for 7 days after study vaccination, from Day 1 (day of vaccination) through Day 8 (for a total of 8 days).

All participants will be given a standard digital thermometer for measuring daily temperatures, a ruler for measuring the size of injection site reactions if any, and an eDiary to capture reactogenicity. All participants will be asked to report on signs and symptoms of solicited ARs ([Table 4](#)) for 7 days following study vaccination and whether medication was taken to relieve the symptoms. Investigators will report on solicited ARs that are ongoing beyond the eDiary

reporting period (ie, 7 days following study vaccination) through to resolution. Solicited ARs should not be reported as unsolicited AEs during the 7 days following vaccination, unless they fulfill the criteria for SAEs or MAAEs. If a solicited AE has not resolved by Day 8, the solicited AE will be reported as “ongoing” in the eDiary and the investigator or designee must obtain the stop date from the participant to record in the eCRF.

Table 4 Predefined Solicited Adverse Reactions for Reactogenicity Assessment

Injection Site	Systemic
Injection site pain	Fever
Injection site erythema/redness	Chills
Injection site swelling	Headache
	Myalgia (muscle aches and pains)
	Fatigue (physical or mental tiredness)

Severity will be assessed for solicited ARs by the participant according to toxicity grading scales modified and abridged from the US FDA Guidance on Toxicity Grading Scale for Healthy Adult and Adolescent Volunteers Enrolled in Preventive Vaccine Clinical Trials ([US FDA 2007](#)) as defined in [Appendix B 4](#).

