9.4.3 Safety

Each solicited AR will be summarized overall and by study arm, study day, and severity grading. In addition, the number of days participants reported experiencing each event will be

presented. The duration of solicited ARs will be calculated as the last day of the AR – the first day of the AR + 1. If the event is ongoing on Day 8, the total number of days will include the days beyond Day 8 through the stop date for the event.

An overall summary of safety will be presented by study arm, including the number and percentage of participants who experience at least one AE (including immediate AEs), SAEs, AESIs and MAAEs. Summaries will present number and percentage of AEs in the categories listed that are related to study intervention as assessed by the Investigator, severe in intensity, serious, and resulting in death. A listing will cover details for each AE.

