In separate tables, the number and percentage of participants reporting solicited adverse reactions will be summarized overall and by study day (Day 1 to Day 8), and by maximum severity. In addition, the time to onset and duration of each solicited AR, in days, will be summarized descriptively, including the number and percentage of participants who experience an AR with duration ≤ 4 days. The denominator for the percentage of participants who experience an AR with duration ≤ 4 days will be the number of participants reporting the

associated AR. Injection site and systemic solicited ARs will be reported along with the overall solicited AR summary by maximum severity.

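### Solicited reactions ongoing at Day 8 whose stop date is never obtained are left out of the duration statistics, which biases the mean and maximum downward, probably by little

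*SAP*

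**What the plan says.** SAP 4.6.2.1 (Adverse Events, Definitions and Derivations) sets the formula: "The duration of solicited ARs will be calculated as the last day of the adverse reaction", minus the first day, plus 1. For a reaction unresolved at Day 8, the start comes from the eDiary and "the stop date will be recorded in the AE eCRF". If there is no stop date, the rule is: "Participants with a missing stop date for a solicited AR will not be included in the calculation of duration". The sentence does not end there: these participants "will not be included in the calculation of duration and will instead be summarized as missing".

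SAP 4.6.2.2 says that "the time to onset and duration of each solicited AR, in days, will be summarized descriptively". It adds the percentage of participants with duration of at most 4 days, using all participants who report that reaction as the denominator. SAP 3.4 lists the mean, median, minimum and maximum among the standard descriptive statistics.

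The protocol expects long reactions to count in full. Section 9.4.3: "If the event is ongoing on Day 8, the total number of days will include the days beyond Day 8 through the stop date". Section 8.4.6 requires that "the investigator or designee must obtain the stop date from the participant to record in the eCRF", and a footnote to the Schedule of Activities says "Investigators are to follow-up on any solicited ARs that are ongoing at Day 8 through to their resolution". Protocol 8.4.2, however, ends eCRF recording for events unresolved at the participant's last AE assessment.

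Neither document plans a lower-bound, censored or sensitivity summary of duration.

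**The concern.** A missing stop date is not a random gap. If the diary is complete, it shows the last day of any reaction that ends by Day 8. A date has to be sought separately only for reactions still present then. When that date is missing, the plan discards a duration whose lower limit is already known, and the reaction is usually among the longer ones.

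This can happen without any site error. A reaction that never resolves has no stop date when eCRF recording stops. A reaction unresolved at the primary analysis, which follows the last Day 29 visit (SAP 3.2), has none at that cut. Solicited reactions are part of the primary safety objective, and duration is one of their planned summaries. A bare missing count does not tell the reader that the reaction lasted to Day 8 or beyond.

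**Working it through.** The documents give no duration figure, no rate of reactions ongoing at Day 8 and no rate of missing stop dates. There is no planned figure to reproduce, and the sizes below are illustrations.

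**What is known about an excluded reaction.** With onset on Day s and presence on Day 8, duration is at least 8 - s + 1 days: 8 for onset on Day 1, 7 for Day 2, 5 for Day 4, 1 for Day 8. If it is still unresolved at a Day 29 visit, even onset on Day 8 gives at least 29 - 8 + 1 = 22 days. Protocol 2.3.1 reports that reactions in earlier studies mostly lasted under 3 days.

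**Effect on the mean.** Let b be the mean duration of reactions resolved by Day 8, f the share ongoing past Day 8, L the mean duration of those, and m the share of those without a stop date.

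- True mean = (1 - f)b + fL
- Mean under the SAP rule = [(1 - f)b + f(1 - m)L] / (1 - fm)

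Assume b = 2.5 days, f = 2% to 10% and L = 10 to 21 days. The mean under the SAP rule is then too low by:

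- m = 10%: 0.01 to 0.17 days (1-4%)
- m = 30%: 0.04 to 0.51 days (2-12%)
- m = 100%: 0.15 to 1.85 days (6-43%)

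One case in full, with f = 5%, L = 14 and m = 30%:

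- True mean: 0.95 × 2.5 + 0.05 × 14 = 3.075
- SAP rule: (2.375 + 0.05 × 0.7 × 14) / (1 - 0.015) = 2.865 / 0.985 = 2.91
- Missing cases counted at a floor of 8 days: 2.375 + 0.05 × (0.7 × 14 + 0.3 × 8) = 2.985

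The floor recovers part of the shortfall, not all of it. If half of about 70 participants per group report the reaction (35, an assumption), this case implies 35 × 0.05 × 0.3 = 0.53 missing stop dates per group.

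**Effect on median and maximum.** Take 35 reporters with durations of 1 day (8 participants), 2 days (12), 3 days (8), 4 days (2), 5 days (1), 6 days (1) and 12 days (3).

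- All included: mean 111/35 = 3.17, median 2, maximum 12
- One 12-day reaction excluded: mean 99/34 = 2.91, median 2, maximum 12
- All three excluded: mean 75/32 = 2.34, median 2, maximum 6

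**Effect on the percentage lasting at most 4 days.** A reaction with onset on Days 1 to 4 and present on Day 8 has lasted at least 5 days, so leaving it out of the numerator is correct. One with later onset might truly last 4 days or less, and leaving it out can only lower the percentage. With 35 reporters, 30 known to last at most 4 days and 2 missing, the SAP denominator gives 30/35 = 85.7%. Removing the missing cases from the denominator would give 30/33 = 90.9%, but the SAP does not do that.

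**The case against.** The strongest reply is that the plan already guards against this. Reactions ongoing at Day 8 are not excluded as such: sites must obtain the stop date and follow the reaction to resolution, participants return on Day 29, and days after Day 8 count. Excluded cases are visible in the table as missing. Solicited reactions are also tabulated by study day through Day 8, so persistence on Day 8 can be read by group without any stop date. The rule fits the SAP's policy of not computing AE durations from imputed dates, and the study tests no hypothesis. All of this stands, and it is why the effect should be small. It does not cover reactions unresolved when recording ends or at the primary-analysis cut. Nor is the last day known present an imputed end date: it is an observed lower limit.

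A second reply also stands. Missing end days need not come only from ongoing reactions. SAP 4.1.11.1 anticipates participants who complete only 1 to 5 of 8 diary days, and a diary that stops early may leave a short reaction without a known end. The SAP does not say how such cases are coded, and excluding them need not lower the mean.

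Third, averaging minimum values with exact durations still underestimates the mean and mixes two kinds of number. That favours censoring, or showing the minimum beside the complete-case summary and not in place of it.

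**Conclusion.** The point holds as a minor one. Where a reaction was ongoing at Day 8 and its stop date is never obtained, the complete-case mean and maximum are biased downward, and neither document offers a summary that uses the days already observed. The direction assumes that the excluded reactions are longer than the average of those kept. That is secure for early onset and for anything unresolved at Day 29, but not for every reaction that starts on Days 6 to 8. The size depends on the share of missing stop dates, which the documents do not give: 1-4% of the mean at an assumed 10% and 2-12% at an assumed 30%. The maximum can change more, and the median will rarely change.

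A reader might infer three stronger things that the documents do not support:

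- that all reactions lasting past Day 8 are dropped: only those without a stop date are;
- that missing stop dates belong mainly to ongoing reactions: no rates are given, and incomplete diaries are another possible source;
- that the rule narrows a true difference between the non-adjuvanted IVX-A12 and the adjuvanted comparator: that would need the rate of long reactions and of missing stop dates in each group, and neither is given.

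**What to change.** Amend SAP 4.6.2.1 as follows:

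- For a solicited reaction ongoing at Day 8 with no stop date, treat duration as right-censored at the last day known present and give a Kaplan-Meier summary. Alternatively, show its minimum duration (last day known present minus first day, plus 1), flagged as at least that long, beside the complete-case summary.
- Split the missing count into reactions ongoing at Day 8 and other causes, such as an incomplete diary.
- State that participants with a missing stop date stay in the denominator of the percentage lasting at most 4 days.

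The cost is a short change of text and minor programming, with no new data collection. The downside is that some durations are shown as lower bounds. The Kaplan-Meier median will usually match the complete-case median, so the gain lies in the upper tail.

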4.6.2.2 Presentations

All AEs will be listed for each participant.

An overall summary of safety will be presented, including the number and percentage of participants for each category, by study period. The denominator for calculation of percentages for adverse events will be the number of participants in the safety analysis set, who are still ongoing in the study at the beginning of the corresponding study period. The denominator for the calculation of percentages for solicited adverse reactions will be the number of participants who provided a response in the eDiary. Should a participant experience multiple events within a category, the participant will be counted only once for that category, in the category of their most severe or related event (where applicable). The overall summary of safety will be reproduced for each age subgroup category.

Event categories included in the overall summary are as follows:

- Study period: Day 1 to Day 29:
 - Unsolicited Immediate AE
 - Unsolicited immediate related AE
 - Unsolicited immediate severe AE
 - Unsolicited immediate related severe AE
 - Solicited AR
 - Solicited injection site AR
 - Solicited systemic AR
 - Unsolicited AE
 - Unsolicited related AE
 - Unsolicited severe AE
 - Unsolicited severe related AE
 - Unsolicited non-serious AE
 - Unsolicited related non-serious AE
 - SAE
 - Related SAE
 - Death
 - AE leading to study discontinuation
 - MAAE

- Related MAAE
- AESI
 - Related AESI
- Study period: From Day 30 to Day 181
 - SAE
 - Related SAE
 - Death
 - AE leading to study discontinuation
 - MAAE
 - Related MAAE
 - AESI
 - Related AESI
- Study period: From Day 1 to Day 181
 - SAE
 - Related SAE
 - Death
 - AE leading to study discontinuation
 - MAAE
 - Related MAAE
 - AESI
 - Related AESI

If there are at least 10 total events in an AE category (excluding ARs), that category will be presented in a summary by SOC and PT. Summaries by SOC and PT will be based on the study period used for reporting of the AE category. For example, unsolicited AEs would be summarized from Day 1 to Day 29, while SAEs would be summarized from Day 1 to Day 181. Participants with multiple occurrences are counted once per SOC and PT regardless of the number of occurrences. Unsolicited AEs by decreasing frequency on PT, based on the total across vaccine groups, will also be summarized from Day 1 to Day 29.

In separate tables, the number and percentage of participants reporting solicited adverse reactions will be summarized overall and by study day (Day 1 to Day 8), and by maximum severity. In addition, the time to onset and duration of each solicited AR, in days, will be summarized descriptively, including the number and percentage of participants who experience an AR with duration ≤ 4 days. The denominator for the percentage of participants who experience an AR with duration ≤ 4 days will be the number of participants reporting the

associated AR. Injection site and systemic solicited ARs will be reported along with the overall solicited AR summary by maximum severity.

4.6.3 Clinical Laboratory Tests

There are no scheduled clinical chemistry and hematology tests in this study. Such tests may be performed as clinically indicated based on participant health, medical history, and ongoing AEs.

4.6.4 Vital Signs

Body temperature and blood pressure will be captured in source documents, not the eCRF. Therefore, no summaries or listings will be created for these parameters.

4.6.5 Electrocardiogram

There are no scheduled ECGs in this study. Electrocardiograms may be performed as clinically indicated based on participant health, medical history, and ongoing AEs.

Appendix A Preferred Terms for RSV/hMPV Infection

Infection	MedDRA 27.0 Preferred Terms	Preferred Term Code
RSV	Pneumonia respiratory syncytial viral	10035732
	Respiratory syncytial virus bronchiolitis	10038718
	Respiratory syncytial virus bronchitis	10069811
	Respiratory syncytial virus infection	10061603
	Respiratory syncytial virus test positive	10068563
hMPV	Human metapneumovirus test positive	10072859
	Metapneumovirus bronchiolitis	10085548
	Metapneumovirus infection	10066226
	Metapneumovirus pneumonia	10085550

Appendix B Missing and Partial Dates for Adverse Events and Concomitant Medications

If an AE onset date is completely missing, then the AE will be assumed to be post-vaccination and will be included in all applicable summaries, unless the stop date indicates otherwise. If the AE onset date is partially missing, AE dates will be handled using the following imputation rules:

The missing start day will be set to:

- First day of the month of occurrence if the start YYYY-MM is after the YYYY-MM of study vaccination.
- The day of study vaccination, if the start YYYY-MM is the same as the YYYY-MM of study vaccination
- The date of informed consent, if the YYYY-MM is before the YYYY-MM of the study vaccination.

If the start date is missing both the day and month, the start date will be set to:

- The date of the study vaccination, if the start year is the same as the year of study vaccination.
- January 1 of the year of occurrence.

The missing end day will be set to:

- The last day of the month of the occurrence, if the YYYY-MM is after the YYYY-MM of the study vaccination.
- The day of data cutoff date, early study withdrawal date, death date or end of study date if the earliest of these occurred in the same YYYY-MM as the partial end date.

If the end date is missing both the day and month, the end date will be set to:

- The data cutoff date, early study withdrawal date, death date or end of study date if the earliest of these occurred in the same year as the AE onset
- December 31 of the year of occurrence

If the start date is null, the date will be set to:

- The date of study vaccination
- Date of informed consent if the end date is on or prior to the date of vaccination.

If the end date is null and the AE outcome indicates that the event is recovered, the end date will be set to:

- The date of study vaccination, if the start date is prior to the date of study vaccination.
- The earliest of the data cutoff date, early study withdrawal date, death date or end of study date.

If the end date is null and the AE outcome indicates that the event is not recovered, the end date will not be imputed.

The same method will be used for missing and partial start and end dates for concomitant medications.
